Verbal consent will be obtained and accurate email address will be confirmed. Eligible subjects will be randomized using a computer-generated randomization scheme with patients assigned in a 1:1 ratio to either:

Study Group: Telemedicine preoperative counseling with an FPMRS fellow

Control Group: Standard in-office preoperative counseling with an FPMRS fellow

The allocation sequence will be in numerical, sealed, opaque envelopes. An envelope will be retrieved at the time of consent. The surgical scheduler will schedule the patient for their allocated preoperative visit.

Prior to their preoperative visit, participants will be emailed copies of the office ERAS informational booklet and International Urogynecology Association (IUGA) patient information handouts pertinent to their surgery. The preoperative visit at Women's Center for Pelvic Health is a counseling visit to review informed consent. Preoperative medical evaluation is accomplished through the Carolinas Hospitalist Group preoperative clinic or with the patient's primary care provider. Patients who require preoperative medical clearance will be scheduled for a preoperative visit with the Carolinas Hospitalist Group or their primary care provider in addition to their preoperative visit with the Women's Center for Pelvic Health. These visits will be documented in the total office visit data collection.

Women in the Telemedicine group will check in for their preoperative visit via an Atrium Information Systems (IS) approved virtual communication platform at the scheduled date and time. They will undergo preoperative counseling following a standardized checklist format. After telemedicine counseling has concluded, participants will be emailed a REDCap survey link to complete a survey regarding their preparation for surgery. (See Figure 2) If a participant has not completed the survey by the next business day, an email reminder will be sent to their email address on file. If they have not completed the survey within 2 business days, they will be contacted by phone for reminder or survey will be obtained in the preoperative area on day of surgery. If a participant in the Telemedicine group ultimately elects to have an in-office preoperative visit, they will be scheduled for in-office visit and analyzed as intention-to-treat.

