Women in the In-office group will present to WCPH for preoperative in-person counseling following a standardized checklist format. After in-office counseling has concluded, participants will be asked to complete a survey regarding preparation for surgery via a REDCap survey link on an Atrium IS approved iPad prior to leaving the office. (See Figure 2) If for any reason the patient did not complete the survey prior to leaving the office, the survey will be emailed to them in similar fashion as the telemedicine group.

PERIOPERATIVE PERIOD

Participants will present to Mercy Hospital, One Day Surgery Center, or CMC Main Hospital for their scheduled surgery. All participants will receive routine care according to the gynecologic enhanced recovery perioperative protocol. The gynecologic enhanced recovery perioperative protocol is a multimodal perioperative care pathway designed to achieve early recovery after surgery by maintaining preoperative organ function and reducing the physical stress of surgery on the body. This protocol includes many components including allowing patients to drink clear liquids up to 3 hours prior to their surgery, maintaining euvoemia intraoperatively, and early return to normal diet and activity after surgery. All patients undergoing pelvic reconstructive surgery are

scheduled for the enhanced recovery protocol, except for women having only minor procedures such as mid-urethral sling placement or cystoscopy.

POSTOPERATIVE PERIOD

All participants will undergo routine postoperative care. They will be scheduled for an in-office or virtual postoperative visit, on average 1-2 weeks after surgery and then an in-office visit at 6 weeks after surgery per our office standard practice. Following their 2-week postoperative visit, women will be asked to complete the preoperative subsection of the Surgical-CAHPS survey to evaluate patient satisfaction. This will be given to all patients in paper format prior to leaving the office or emailed to them via REDCap survey link. If a patient does not present to their 2-week postoperative appointment, they will be emailed a copy of the preoperative subsection of the S-CAHPS and this will be automatically uploaded into REDCap when submitted by the participant.

Following the 6 week postoperative visit, secondary data will then be extracted from the EMR via manual chart view.

RANDOMIZATION

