An Atrium Health biostatistician will generate a randomization sequence using SAS Enterprise Guide 6.1. A permuted block randomization scheme will be used to assign patients in a 1:1 ratio to Telemedicine visit or In-office visit.

The study will not be blinded.

DATA COLLECTION AND MANAGEMENT

Data Collection Schedule

Case report forms will be developed by the investigators. Data will be collected prospectively per the schedule in Table 1. All study data will be recorded by research staff and securely maintained at the Mercy study site. The data flow will consist of paper data collection for eligibility assessment, baseline data, randomization, intervention group, primary and secondary outcomes, and protocol deviations.

Data will be entered by study staff into REDCap database that will be stored on a secure server at Atrium Health. Web-based survey responses will be linked to REDCap for automatic entry following participant submission of surveys. REDCap (Research Electronic Data Capture) is a secure, web-based application designed to support data capture for research studies providing: 1) an intuitive interface for validated data entry; 2) audit trails for tracking data manipulation and export procedures; 3) automated export procedures for seamless data downloads to common statistical packages; and 4) procedures for importing data from external sources (13).

Each patient will have a unique identification number to which only the principal and sub-investigators will have access. The data collection spreadsheet will not contain any patient identifiers and will be password protected. The master list that links the patients and their study information will be stored separately on a password protected hard drive. A back up copy of the file will be stored on a password protected hospital network drive. All hard copies of study data will be stored in a locked cabinet in the office of the research nurse, which will also be locked.

Table 1. Data Collection Schedule

	Prior to Preoperative visit	Preoperative visit	Period between Preop visit and surgery	Surgery	2 week postop visit	6 week postop visit
Informed consent	X					
Randomization	X					
Travel distance	X					
Internet Access/Usage	X	X				
Other Demographics*	X	X				
Patient Preparedness		X				
Patient Satisfaction					X	
Office visits		X	X		X	X
Cost metrics						X

*Other demographic data includes: Age, Race, Education level, Health literacy score, and number of prior surgeries.

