- d. **Office contacts:** The total number and type of office contact between the preoperative visit and the 6-week postoperative visit will be collected via manual chart review. Type of office contact visits include patient-initiated calls, nurse-initiated calls, scheduled office visits, and add-on office visits.
- e. **Canceled, No-show, and late visits:** If patients call to cancel their appointment this will be considered a canceled preoperative visit. Rescheduled appointment will be noted. Patients who arrive to their visit later than 10 minutes will be considered late for each group. If patients do not present for their visit, it will be considered a No-show appointment.
- f. **Calculated value proposition metrics:** The length of visit will be compared between groups. Office schedules will be analyzed and will determine the percentages of new patient visits and preoperative visits. If preoperative visits are replaced with new patient visits over a month, based on institutional data, anticipated new operative cases and projected revenue impact on the health care system will be determined. Costs of video based virtual visit platform will also be calculated.

STATISTICAL CONSIDERATIONS

Statistical Methods

The primary analysis will compare summary scores of preparedness between both study groups. Non-inferiority of virtual visit compared with in-person visit

would be claimed if the upper limit of the one-sided 95% confidence interval for the mean differences of scores between two groups will not exceed the pre-specified margin of 9 points. Descriptive statistics will be calculated to assess level of preparedness for each question. Secondary outcomes, demographics, and other baseline variables will be compared between the two groups using the Chi squared test or Fisher's exact test for categorical data, Student's t test for normally distributed data, and the Wilcoxon rank sum test for ordinal data or continuous data that are not normally distributed.

Sample Size Calculation

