12. Please select the type of visit you had:

- ¹ In-office visit
² Virtual visit

13. How satisfied are you with the visit that you had before your surgery?

- ¹ Very satisfied
² Satisfied
³ Neither satisfied or dissatisfied
⁴ Not satisfied
⁵ Very dissatisfied

14. How would you rate the level of convenience of the visit (virtual or in-person)?

- ¹ Very convenient
² Convenient
³ Neither convenient or inconvenient
⁴ Not convenient
⁵ Very inconvenient

15. If you need to have surgery in the future, would you like to have this type of visit again?

- ¹ Yes
² No
³ Not sure

16. Would you recommend the type of visit you had to a friend?

- ¹ Yes
² No
³ Not sure

17. If in the future our clinic offered the option to have a preoperative visit using virtual visit technology or an in-person clinic visit, which would you prefer?

- 1 Virtual visit
- 2 In-person clinic visit
- 3 No preference

18. What types of technology have you used in the past to access health care services or personal health information? Select all that apply:

- 1 Video conferencing (virtual visit)
- 2 Email
- 3 Text messaging
- 4 Patient Portal (e.g. My Carolinas)
- 5 Mobile health (accessing health services or personal health data via mobile devices)
- 6 Other: _____
- 7 None

The following questions will help us determine comfort level with health information.

19. How often do you have someone (like a family member, friend, hospital/clinic worker, or caregiver) help you read hospital materials?

- 1 None of the time
- 2 A little of the time
- 3 Some of the time
- 4 Most of the time
- 5 All of the time

20. How often do you have problems learning about your medical condition because of difficulty understanding written information?

- 1 None of the time
- 2 A little of the time
- 3 Some of the time
- 4 Most of the time
- 5 All of the time

21. How confident are you filling out forms by yourself?

- 1 Extremely
- 2 Quite a bit
- 3 Somewhat
- 4 A little bit
- 5 Not at all

Figure 3. Postoperative visit survey

Your Privacy is Protected. All information that would let someone identify you or your family will be kept private. The Women’s Center for Pelvic Health will not share your personal information with anyone. Your responses to this survey are also completely **confidential**.

Your Participation is Voluntary. You may choose to answer this survey or not. If you choose not to, this will not affect the health care you get.

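### Prior technology use (survey item 18) is asked after the randomised visit with no cut-off date, so telemedicine participants can count the study visit itself as prior video use

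*Combined protocol and SAP*

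**What the plan says.** Figure 2, item 18, asks "What types of technology have you used in the past to access health care services or personal health information". Respondents tick all options that apply, and the first is video conferencing, with virtual visit in brackets. Items 12-17 come just before it and concern the visit just completed; item 12 labels the telemedicine visit a virtual visit. Items 19-21 follow under the line "The following questions will help us determine comfort level with health information".

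Both arms receive this survey after counseling. The Preoperative Period section says of the telemedicine arm: "After telemedicine counseling has concluded, participants will be emailed a REDCap survey link to complete a survey regarding their preparation for surgery". For the in-office arm: "After in-office counseling has concluded, participants will be asked to complete a survey regarding preparation for surgery", on an iPad before leaving.

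The Table 1 footnote places health literacy among the demographics: "Other demographic data includes: Age, Race, Education level, Health literacy score, and number of prior surgeries". Table 1 marks both that row and the Internet Access/Usage row in two columns, before the preoperative visit and at it. Data Collection and Management also mentions paper collection of baseline data, without listing its contents.

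Statistical Methods says: "Secondary outcomes, demographics, and other baseline variables will be compared between the two groups". No adjusted, subgroup or responder versus non-responder analysis using these variables is described.

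**The concern.** A description of prior experience should not be open to change by the assigned treatment. Item 18 is open to it in one arm only. A woman who has just finished a telemedicine visit has used video conferencing for health care, so ticking the first option is a literal and correct answer. The error runs one way: it can only raise reported video use in the telemedicine arm.

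Two things are at stake. First, the group comparison could suggest that randomisation produced arms with different telehealth experience when it did not, or could conceal a real difference. A reader might then ask for adjustment on item 18, which would mean conditioning on a variable that the assignment itself had altered. Second, the trial could not say how many enrolled women were already used to video visits, which matters for judging to whom the result applies.

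Items 19-21 raise a separate and smaller question. They sit inside the survey that carries the primary outcome. If they are asked nowhere else, a woman who never returns the survey has no literacy score, and non-responders cannot be described on literacy.

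**Working it through.** **The plan's own figure.** The plan states no figure for prior technology use. The only planned number used here is 45 evaluable women per arm (Sample Size Calculation). It reproduces from margin 9, SD 15, one-sided alpha 0.025 and power 0.8: 2 × (1.960 + 0.842)² × 15² / 9² = 43.6, so 44 by normal approximation. The t-test calculation gives 45, with power 0.804.

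**Inputs for item 18 (assumptions).**
- p = true prior video use, the same in both arms; range 10-50%.
- f = share of telemedicine-arm non-users who tick the option because of the study visit; range 0.25-1.
- n = 45 respondents per arm.

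**Formulas.** Reported use is p in the in-office arm and q = p + (1 − p) × f in the telemedicine arm. The false gap is q − p = (1 − p) × f. The chance that a two-sided 5% test of two proportions calls it significant is Φ{[(q − p)√n − 1.96√(2m(1 − m))] / √[p(1 − p) + q(1 − q)]}, with m = (p + q)/2.

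**Worked case.** With p = 0.20 and f = 0.5, q = 0.20 + 0.80 × 0.5 = 0.60 and the gap is 40 points. With m = 0.40, the chance is Φ[(0.40 × 6.708 − 1.96 × 0.693) / 0.632] = Φ(2.10) = 0.98.

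**Results.** Each cell gives reported telemedicine use, the gap in points, and the chance of a significant difference.

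| True p | f = 0.25 | f = 0.5 | f = 1 |
|---|---|---|---|
| 10% | 32.5%; 22.5; 0.75 | 55%; 45; >0.99 | 100%; 90; about 1 |
| 20% | 40%; 20; 0.55 | 60%; 40; 0.98 | 100%; 80; about 1 |
| 30% | 47.5%; 17.5; 0.40 | 65%; 35; 0.93 | 100%; 70; about 1 |
| 50% | 62.5%; 12.5; 0.22 | 75%; 25; 0.69 | 100%; 50; about 1 |

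For p of 20-50% the gap is 25-40 points at f = 0.5 and 50-80 points at f = 1. With 41 respondents per arm instead of 45, the lowest chance moves only from 0.22 to 0.20.

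**Masking.** Suppose true prior use were 20% in the telemedicine arm and 50% in-office. Reported use would be equal when 0.20 + 0.80 × f = 0.50, that is f = 0.375. A real 30-point deficit would then disappear.

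**Literacy, if Figure 2 is the only source.** Two ceilings follow from the planned allowance. The plan's numbers give 59 − 45 = 14 per arm, or 28 in all. The stated 30% applied to 118 gives 35.4, or about 35 in all. (The two differ because 59 is 45 × 1.3 rounded up; that is a separate matter.) Both count every planned dropout as a survey never returned.

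**The case against.** The strongest reply is that Table 1 already schedules Internet Access/Usage and the demographics, health literacy included, before the visit as well as at it, and that a paper baseline form is named whose contents are not reproduced. This stands in part. It rules out saying that no pre-visit collection is planned. It does not settle the point: the only instrument shown for these questions is the post-visit survey, and the plan does not say which value would serve as baseline if there were two. The plan also never names item 18 as a baseline variable; linking it to the Internet Access/Usage row is the natural reading, not a stated one.

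Four stronger inferences are tempting, and the documents do not support them:
- *Survey non-responders have no literacy score.* This is true only if Figure 2 is the sole source, which is suggested but not stated.
- *Fourteen women per arm will lack these data.* This equates dropout with non-response. The plan provides an iPad before leaving, an email reminder, and then a phone reminder or collection on the day of surgery. Age, race, education and prior surgeries are not asked in Figure 2, so non-responders might still be described on those.
- *The literacy answers are biased by the visit.* Items 19-21 ask about general habits that one counseling visit is unlikely to change. Contamination concerns item 18.
- *The primary result is affected.* These variables enter no primary analysis.

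It is also fair to say that the 100% end is extreme. It needs every non-user to tick the option, and the plan lets telemedicine participants switch to an in-office visit while staying in their assigned group; those who switch would have had no study video visit to count.

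**Conclusion.** The point holds for item 18. As written, it measures past technology use after the randomised visit, with no cut-off, and in a way that can inflate reported video use in the telemedicine arm alone. Under assumed true prior use of 20-50% in both arms, the false gap is 25-40 points if half of non-users count the study visit and at most 50-80 points if all do. Under the mildest assumptions examined (50% prior use, a quarter ticking) it is 12.5 points, with about a 22% chance of a nominally significant difference. The direction of the error follows from the text; its size rests on assumptions.

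For items 19-21 the conclusion is conditional: women who never return the survey lack a literacy score only if no pre-visit form asks these questions.

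The non-inferiority estimate, margin and sample size do not change. The consequence is confined to the description and comparison of the groups. The correction is still worth making before enrolment, because an uncontaminated answer cannot be reliably recovered once the visit has taken place.

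**What to change.** Preferred: ask items 18-21 at verbal consent, before the envelope is opened, when the email address is already being confirmed, and remove them from the post-visit survey. Minimum: keep item 18 where it is but word it as *before this preoperative visit*.

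If the items are moved to consent, use the pre-randomisation values for the baseline table and for any description of women who do not return the survey. Align Table 1 by naming the form that supplies each of Internet Access/Usage and health literacy score, and marking the time point that counts as baseline. If the paper baseline form already asks these questions, say so in the plan and state that its values are the ones used.

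Cost: a few extra minutes at consent and a change to the REDCap form. With the preferred option, the post-visit survey becomes four items shorter.
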